### ***Adverse Event Reporting***

In the case of an adverse Effect (AE) or a Serious Adverse Effect (SAE), a written report of the AE or SAE will be prepared for the Chair of the IRB at the Central TX VAHCS. Any such AEs or SAEs will be presented to the full IRB committees. SAEs will be reported within 24 hours. Examples of serious adverse effects include death, life-threatening adverse events,

suicide attempts, and inpatient hospitalization. The report of such AEs or SAEs will include whether they were expected or unexpected, a rating of severity of the event, a brief narrative summary of the event, a determination of whether a causal relationship existed between the study procedures and the event, whether the informed consent should be changed as a result of the event, and whether all enrolled participants should be notified of the event. The annual progress reports to the IRB require summary information regarding all AEs and SAEs occurring during that year. A medical monitor who is independent of the research will be named. The medical monitor will be called upon to review all AEs and SAEs, and to provide input regarding the possible connection to the study protocol.

## **Risks / Benefits Assessment**

### ***Risks/Benefits Assessment:***

**Foreseeable risks:** There are four major areas of low to moderate risk associated with participation in the proposed study: 1) It is possible that some women may feel coerced into participating in the research. 2) There is risk to confidentiality and loss of privacy. We will be collecting considerable information about the participants that may create some distress and could cause social and psychological risk if released inappropriately. 3) Research participants may decompensate when completing the assessments included in the research proposal. 4) Participation may place women at risk for further victimization if an abusive partner finds out about their participation in the research. The procedures we will use to minimize these risks are described below.

Data and safety monitoring will take place to assure the safety of subjects. All participants will be reminded that their participation is voluntary and that they can withdraw at any time without penalty. Additionally, the risks described above will be minimized by the following procedures:

1. We will minimize the risk of potential coercion by following standard procedures for obtaining informed consent. We will begin this process during the intake for the screening phase and the trial phase, where we will clarify the nature of the study and possible alternatives upfront. Prior to enrolling women in the research, we will fully explain the study procedures, risks, benefits, and alternatives to women. Participants will be reminded that study participation is voluntary and that refusing to participate or withdrawing from the study at any time will not impact in any way their relationship to the Central Texas VA or any other VAMC, or existing services they receive within the community. Veterans will have the opportunity to discuss any uncomfortable feelings with the assessment or intervention with the research assistant who will be available during both the assessment and intervention. The Veteran will also be informed that the veteran's well-being and safety takes priority over research considerations. Furthermore the veteran will be informed that should they experience any problems, they should report them to the research assistant or to the principal investigator of this study. All reimbursements for participating will be commensurate with participants' time required for participating in the research.

2. We will minimize potential risks due to loss of confidentiality of research data by having all information collected and handled by research staff trained to deal appropriately with sensitive clinical issues. All participants will be informed about the limits of confidentiality concerning suicidal intent, homicidal intent, suspected child abuse, and suspected elder abuse. All information will be treated as confidential material and will be available only to research

staff. All information will be kept in locked file cabinets in locked offices. Computer data files will be available only to authorized personnel and no names or obvious identifying information will be stored in data files. Information, including assessments, collected in this study will not be entered into participants' medical records at the PVAMC. No participant will be identified in any report of the project. Veterans will be informed that federal and non-federal monitoring agencies such as the Department of Veterans Affairs may access the veteran's research records related to this study to monitor the security of the trial. Furthermore, veterans will be informed that complete confidentiality cannot be promised to subjects, particularly to subjects who are military personnel, because information bearing on their health may be required to be reported to appropriate medical or command authorities. Written consent will be obtained to contact other persons for the purpose of locating the participant for follow-up and participants can refuse or revoke such consents. All study personnel who handle data will be trained in confidentiality policies and procedures.

Participants in the open trial or randomized control study phase will update their contact information at each follow-up interview to ensure that this information remains appropriate. To further protect participants, a Confidentiality Certificate will be sought after the grant has been funded. Potential subjects will be informed that a Certificate of Confidentiality has been obtained for this project and that this certificate will protect the investigators from being forced to release any research data in which participants can be identified, even under court order or subpoena, although this protection is not absolute. Potential subjects will be informed of the situations in which they may not be protected under the Certificate of Confidentiality. No information about participants will be released without their permission or where required by law.

Audio recording of informant interviews and exit interviews is also needed to produce structured transcripts and identify themes. This is accomplished through the use of digital audio recorders, which can hold hundreds of hours of voice recordings. These digital recordings will be uploaded to the CTVHCS secure research server (W drive). Participants will be asked to give informed written consent to audio recording at the time of study entry. To assure the confidentiality and protection of participants with respect to audio taping, the following steps will be taken: a) each recording will be labeled with the participant's study identification number, and the recording date; b) all recordings will be stored in a restricted folder on the secure research server CTX W drive c) access to the audio recordings will be limited to the specially trained staff who will code the recordings and create structured transcripts; d) once the recordings are transcribed they will be stripped of all identifiers for the purposes of analyses; at the end of the study, the recorder will be given to OI&T for sanitization.

All data and medical information obtained about the veteran, as an individual, will be considered privileged and held in confidence; the veteran will not be identified in any presentation of the results. Assessments and intervention sessions will occur at the CTVHCS. Veterans will be informed that their VA medical records will note their enrollment in a research study with a copy of their consent form attached. In addition, their attendance at each intervention session will be noted in their medical records. This will include, if applicable, any safety issues (e.g., suicidal or homicidal statements they made) and how these were addressed in treatment. The veteran will be informed that none of the other data from this study will be included in their Medical records. All study data stripped of identifying information, will be locked in a file cabinet. Records will be maintained per Veterans Affairs Record Control Schedule 10-1. All of the study data will be coded without the use of the veteran's name and social security number and will be done in accordance with the law. Research information about

the veteran will remain in locked private research files and will be available only to staff connected with this study or individuals involved in human subjects protection. Any reports or publications of this study will not include information that could be used to identify the veteran.

All forms with participant information will be marked with a code number and not with the participants' name. The PIs will keep the link between the participant code number and name in a separate restricted folder on the CTVHCS secure server (W drive). Information that might potentially allow an individual participant to be identified will not be allowed in any publications or reports sent to individuals outside the study.

In accordance with VA policy, incidents such as theft or loss of data or storage media, unauthorized access of sensitive data or storage devices or non-compliance with security controls will be reported immediately to the ISO and PO.

**3.** We will minimize the risk of distress. Participants from our target population face the risk of increased distress during assessment procedures, during the control condition, or during the experimental condition. The potential that veterans might develop uncomfortable feelings during assessments and the intervention will be discussed during the consent process. Possible distress due to sensitive items will be noted clearly in the informed consent information sheet (for screening) and in the written informed consent form (for participants). Participants will be informed that they can refuse to answer any question or stop the assessment or intervention at any time. They will be informed that they can choose to resume the assessment or intervention or refuse to participate further. Veterans will have the opportunity to discuss any uncomfortable feelings with the assessment or intervention with the research assistant who will be available during both the computer-based assessment and intervention. Moreover, clinical backup will be provided during all assessments and during the intervention phase of the study by a licensed clinician to help facilitate any stabilization and referral process for participants who decompensate during study procedures. The need for additional services will also be monitored during all follow-up assessments. The veteran will also be informed that the veteran's well-being and safety takes priority over research considerations. Furthermore the veteran will be informed that should she experience any problems, she should report them to the research assistant or to the principal investigator of this study.

To further address possible distress due to sensitive items, participants will be asked by the computer program if anything the computer has asked or done is making them feel upset right now. The computer program will notify the research team at completion of the screening, intervention session, or assessment, if any participant answers yes to this question, in addition to notifying the research assistant (RA) if the participant endorsed any items indicative of possible need/desire for further assistance. (Note that the computer program will not provide details regarding any answers, only that there is a need to follow-up with the participant verbally to evaluate the need for assistance). At a minimum, all participants indicating some distress will be given a list of referral and resource options.

Any participant verbalizing or showing signs of distress will be asked to remain in the assessment or intervention setting until their distress is at a manageable and comfortable level. No participant judged to be in danger of harm to self or others will be allowed to leave the study setting unaccompanied. All study personnel who interact with study participants (including phone contacts) will have been professionally trained to respond to negative emotions if these should occur and to access emergency services if necessary. All participants will be reminded of appropriate safety procedures including providing them with emergency contact numbers such as 911 and the number for the Veterans Crisis Line. All research personnel will be trained in the

protocol for homicidal or suicidal risk and research procedures for these situations. A licensed clinician will be available at all times by phone. Research staff will contact the licensed clinician if there are any safety concerns.

The assessment instruments and program techniques are commonly used in research and clinical practice. We will minimize distress by presenting questions/program techniques in a supportive manner, assuring participants that they may refuse to answer questions that make them uncomfortable, and may terminate the assessment and/or intervention at any time. Any participant verbalizing or showing signs of distress will be asked to remain in the assessment or treatment setting until their distress is at a manageable and comfortable level. No participant judged to be in danger of hurting him/herself or others will be allowed to leave the study setting unaccompanied. All study personnel who interact with study participants will have been professionally trained to respond to negative emotions if these should occur and to access emergency services if necessary.

Moreover, clinical backup will be provided during all assessments and during the intervention phase of the study by a licensed clinician to help facilitate the stabilization and referral process for participants who decompensate during assessment procedures. [name] is a licensed clinical psychologist and she will be available by phone or in person during study assessments. Since the study will take place in women's primary care during normal operating hours, access to emergency resources will be readily accessible. The need for additional services will also be monitored during all follow-up assessments. Participants will be formally assessed at intake and then at the 2- and 4-month follow-up period. If a participant indicates distress during any phase of the study, the clinical back up will be contacted to facilitate the stabilization and referral process. Women veterans who report significant suicide or homicidal risk will be referred for appropriate additional care, but will remain in the research protocol. During any phase of the study, women who report significant homicide or suicide risk will be immediately referred for evaluation for psychiatric admission at the closest emergency department. All participants will be eligible for emergency services through the CTVHCS.

**Referral to treatment and counseling during the study.** After screening and prior to randomization, all study participants will receive a list of appropriate referrals (e.g., 24-hour hotlines for sexual trauma and intimate partner violence (IPV), as well as mental health and substance abuse treatment). Additionally, no referral, or counseling will be withheld in any way at any time during the study. At follow-up assessments, any participant who screens positive for heavy drinking or PTSD will be referred for appropriate clinical care, for example consults will be placed for further care if the Veterans desires. In addition to referrals within the VA, we have a list of free or low-cost substance use and mental health treatment clinics in Central Texas.. Likewise, at follow-up assessments, any participant who reports current ST and/or IPV will be provided with information on ST/IPV and a list of local IPV/ST resources and an offer for contact with the local VA Domestic Violence coordinator or Women Veterans Program Manager.

4. We will minimize the risk of study-related partner violence. Women who have abusive partners may be at increased risk for abuse if he or she were to find out about the woman's participation in the research project. The measures suggested by Sullivan and Cain (2004)[22] will be taken to maximize participant safety throughout the research.. Outgoing phone calls will go through the VA landline phone system which is identified at the receiving end as a general VA number not specific to any VA Hospital department. All incoming phone calls will go through a study specific cell phone. This line is answered, "The Women's Program," and partner violence is never mentioned. Details of the research are not provided to anyone other than the actual participant. During each contact, participants will first be asked if it

is a safe time to speak. Safe contact for follow-up assessments will be negotiated at each stage of the research. Both written and verbal contacts will be vague. Follow-up interviews will be scheduled at VA primary care or in the research space at the Center of Excellence. Safety plans will be negotiated up front (e.g., code words, cover story for reason for interview) if ever the abuser were to interrupt a phone call or assessment. Any handouts with important information (e.g., hotline numbers) will be available in wallet size copies without any reference to the study or name of organization. Participants' safe contact information will be updated monthly to determine if the contact information they previously provided is still accurate and safe. Participants will be given contact information for the research team and/or interventionist and asked to let us know if the contact information they provided is no longer safe. A licensed clinician will be available for consultation on difficult cases at all times by phone. If a woman discloses that she is in an abusive relationship, she will be provided with the battered women's crisis line for emergencies, referrals to battered women's shelters, and told how to obtain a restraining order and she will be connected with the VA women's health coordinator and domestic violence coordinator for additional assistance. All participants will be reminded that if they are currently in an abusive relationship, their partner could find the informed consent form from the study and this could place them in danger because it makes mentions of partner violence. They may wish to store it/dispose of the form in a secure location.

If the partner of the participant is also abusing her child[ren], then the interventionist, supervisor, or research staff person involved will let the woman know that she as the mother is responsible for protecting her child[ren] and if her partner hurts them and she fails to call child welfare or the police, she could be charged with neglect and her children could be taken away. The supervisor/research staff will encourage the woman to call child welfare herself as child welfare is more likely to view the woman favorably under these circumstances. The research personnel involved will provide the woman with the relevant phone number/s. The research personnel involved will let the woman know that she/he will be calling child welfare her/himself because it is the law. This same procedure will be followed for any other case of suspected child abuse.

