### **Measures**

(See appendix for measures) All assessments for this study will be completed on a laptop/tablet computer through web administration at in-person sessions held in women's primary care or dedicated research space at the VA in Waco and Temple.

**Overview of assessments:** Standard instruments will be administered to gather demographic data and to assess key constructs of ST, PTSD, IPV, alcohol use, as well as resource and treatment utilization. If other relevant constructs are identified in informant interviews, we will add measures to assess these constructs during the initial randomized control trial. Participants will complete screening assessments, and individuals randomized to the SHE intervention or SR

(control condition) will complete assessments at a 2- and 4-month follow-up. One of the two research assistants who is not involved in recruitment will be available during the assessments and masked to the intervention condition. If a participant is called for her medical appointment during her screening or assessments, the research assistant will offer to continue after her medical appointment or schedule a return visit.

All assessments are well established, with adequate reliability and validity, well-matched to our program components and aims. The baseline battery is designed to minimize assessment with the control group in order to take into account growing concerns regarding the motivational properties of assessment, leading to substantial Type II error in other MI-based intervention studies. The baseline assessment will occur immediately following the consent procedures, and will be self-administered on a laptop computer. Items from the screening and baseline assessments that will be used to generate the personalized feedback report (PFR) used in the intervention modules are marked with an asterisk (\*).

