For participants in the trial, we will also conduct a chart review using the VA Computerized Patient Records System to assess for mental health appointment attendance before and after the trial. This will entail documenting the number of mental health appointments attended at VA 4 months before the trial and 4 months after. The purpose of this information is to objectively document whether SHE increases engagement in VHA mental healthcare.

**Assessment of acceptability:** Satisfaction with CIAS Software Scale (SCSS) assesses participant satisfaction on items tapping on likeability, ease of use, level of interest, and respectfulness using a 1 – 5 Likert scale (1 = low, and 5 = high). This scale will be administered after every SHE module. The Client Satisfaction Questionnaire (CSQ) is an 8-item questionnaire which assesses the participant’s satisfaction with the intervention. The scale has good psychometric properties and correlates highly with other intervention measures. Only participants in SHE will complete these two measures immediately after the intervention.

**Measures of family and relationship functioning:** Prior research on Veterans has suggested that family and relationship functioning may influence treatment engagement, therefore we will include such measures as a covariate in analyses and to examine how family functioning may predict treatment completion, appointment attendance. The Quality of Marriage Index (QMI; Norton, 1983) will be used to assess relationship distress (6 items). The Family Assessment Device 12 (FAD; Epstein, Baldwin, Bishop) is a brief measure of general family functioning.

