### ***Randomization (RCT only)***

The computer program will randomly assign participants to condition and the research assistant will remain blinded.

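### The VA record used to count mental health visits shows who received SHE, the count has no anchor date or exclusion of study contacts, and the research assistants' masking is stated inconsistently

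*Combined protocol and SAP*

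**What the plan says.** **The record.** Item 2 of the Risks/Benefits Assessment lists what enters the VA medical record: study enrolment with the consent form, any safety issues, and, for the intervention, "their attendance at each intervention session will be noted in their medical records". No other study data are to be entered.

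**The count.** The treatment-utilization part of Measures says "we will also conduct a chart review using the VA Computerized Patient Records System". The task is "documenting the number of mental health appointments attended at VA 4 months before the trial and 4 months after", and the reason given is: "The purpose of this information is to objectively document whether SHE increases engagement in VHA mental healthcare". Secondary outcome (Aim 4b) places this count beside the Treatment Services Review and the Effectiveness in Obtaining Resources scale, both self-report.

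**Masking.** Randomization (RCT only) has the computer assign the condition and says "the research assistant will remain blinded". The overview of assessments under Measures says: "One of the two research assistants who is not involved in recruitment will be available during the assessments and masked to the intervention condition". Item 3 of the Risks/Benefits Assessment refers to "the research assistant who will be available during both the computer-based assessment and intervention", and item 1 says much the same. Section 6 (Survey/Intervention Administration) has each participant set up with a screening, assessment or intervention session, so whoever does this knows the session type. Retention allows follow-up assessments by phone with a staff member.

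**The concern.** Two separate matters are at stake.

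The first is the visit count. It is offered as the objective check on whether SHE brings women into VA mental health care, because the other utilization measures rest on what women report. That value is reduced if the reader of the chart knows the arm and must decide, without a written rule, which encounters to count and from which date. One kind of entry, the SHE session note, can occur in one arm only.

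The second is the masking of the research assistants. Most data are entered by the women themselves on a computer, which limits a staff member's influence. The phone option removes that protection for some follow-ups, and those follow-ups include the self-report measures behind the primary outcome. Who is masked at months 2 and 4 therefore needs a clear answer.

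**Working it through.** The documents give no mean, standard deviation, sample size or power for the visit count, so there is no stated figure to reproduce. The check is mainly textual, followed by an illustration of size.

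**1. Does the record reveal the arm?** Enrolment and the consent form are filed for everyone. Session attendance is filed only where there are intervention sessions, and the control condition is screening and referral only. A SHE attendance note therefore identifies a SHE participant.

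**2. What protects the count?** The plan does not say who reviews the chart, whether that person is masked, which encounters qualify, or whether study contacts are left out.

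**3. Could SHE sessions fall in the window?** The SHE Intervention section puts the first module after baseline and any others at a session within one week. There are two readings of the window:
- If it starts when trial participation ends, the SHE sessions lie outside it. The count would then cover a period after the 2- and 4-month follow-up to which Aim 4 refers.
- If it starts at baseline or randomization, the SHE sessions lie inside it.

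**4. How large could the artefact be?** The Power Analysis projects equal numbers (50/50/50) with one, two and three risks. One risk means one session. Two or three risks mean the first session plus one more. With full attendance:

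(1 + 2 + 2) / 3 = 5/3 ≈ 1.67 sessions per SHE woman, against 0 in control.

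This is the artefact if every session is counted as a mental health visit and the window starts at baseline. If none is counted, it is 0.

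For scale, take 126 retained women, 63 per arm (the plan says half receive no intervention). Assume no true effect, a two-sided alpha of .05 and a normal approximation:

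SE = SD × √(2/63); P(significant) = Φ(δ/SE − 1.96) + Φ(−δ/SE − 1.96).

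The SD of visits is not in the documents. I assume 4 to 10.

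| Assumed SD | SE | δ/SD for δ = 1.67 | P(significant), δ = 1.67 | P(significant), δ = 0.5 |
|---|---|---|---|---|
| 4 | 0.713 | 0.42 | .648 | .108 |
| 6 | 1.069 | 0.28 | .344 | .075 |
| 8 | 1.425 | 0.21 | .215 | .064 |
| 10 | 1.782 | 0.17 | .155 | .059 |

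With δ = 0 the probability is the nominal .05. The δ = 0.5 column is an arbitrary case of partial miscounting.

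**5. Do the masking statements agree?** Taken alone, the Randomization sentence blinds the research assistant without qualification. Items 1 and 3 of the Risks/Benefits Assessment make the research assistant available at both assessments and SHE sessions. Anyone on hand at a SHE session, or setting one up, knows the arm. The overview of assessments describes two assistants, one of them masked. This resolves the conflict only if the masked one has no part in SHE sessions, and the plan does not say so. Baseline is also an assessment and the first module follows it, so a masked assistant serving at baseline could see who goes on to a module.

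**The case against.** The strongest reply is that little of this is shown to bias anything. Much of that reply stands.

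- **SHE as counted care.** A reader might infer that SHE sessions will be scored as mental health visits. The documents do not support that. The outcome is mental health appointments, SHE is held in primary care or research space, and it is nowhere called a mental health appointment. What is missing is a rule that settles the question.
- **The masked assistant at SHE sessions.** A reader might infer that the masked assistant attends them. The text says only that a research assistant is available, and there are two assistants. Nor would such attendance unblind the chart count, because the plan does not say who does the review.
- **Treating clinicians.** They could see the session notes, and a reader might infer a bias toward SHE. The direction is not established. Control women are offered facilitated consults and warm hand-offs, and SHE itself encourages women to talk to their providers.
- **Payment.** A reader might infer that the completion bonus unmasks staff. It is the same amount in both arms and is paid after the 4-month assessment, so a yes/no eligibility flag is enough.
- **Judgement and weight.** Counting attended appointments leaves less room for judgement than rating symptoms. The count is one component of a secondary outcome, and the Power Analysis puts estimating an effect size ahead of significance.

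The last point does not remove the concern. A miscount distorts an effect size as readily as a p-value, as the δ/SD column shows. The reply also leaves untouched the visible arm, the missing anchor and exclusion rule, and the unreconciled masking statements.

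**Conclusion.** The concern holds in limited form. The record that supplies the visit count shows which women attended SHE, and the plan provides no masked abstraction, no exclusion of study contacts and no anchor date. The possible artefact runs from 0 to about 1.67 visits per SHE woman. The upper end is a ceiling that rests on the projected equal split of risks, full attendance, one further session for all remaining modules, every session counted, and a window starting at baseline. The false-positive probabilities also depend on assumed SDs and describe the worst case, not an expected result. Any effect of unmasked abstraction alone cannot be sized from the documents.

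The masking conflict is a separate matter and matters chiefly for phone follow-ups. The chart problem does not touch the primary number-of-risks outcome. This is a cheap improvement worth making before outcome data are collected.

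**What to change.** 1. Replace the manual chart review with a dated clinic-code extract by study ID, without arm, run by the study analyst who already pulls VA administrative data for recruitment (second strategy under Screening).
2. List the clinic codes that count as mental health visits, and exclude all study encounters, both SHE sessions and assessments.
3. Anchor both 4-month windows to the randomization date. This puts the SHE sessions inside the later window, so the exclusion in step 2 is essential.
4. Reconcile the overview of assessments, Randomization, and items 1 and 3 of the Risks/Benefits Assessment. One existing assistant supports SHE sessions and is described as unmasked. The other is masked and conducts the 2- and 4-month assessments, including those by phone.

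The cost is protocol wording, an assignment of roles among existing staff and one data pull, subject to the usual VA approval. No sample size or power figure changes. The downside is that coded data may misclassify a few visits that a chart reader would catch, similarly in both arms. Filing identical visit notes in both arms is not an adequate substitute: the number and dates of the notes would still reveal the arm.
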